### **2. Medical records and vital parameters:**

All evaluations commenced 30 s after delivery and terminated at 10 min. For each infant, the 1st and 5th min Apgar scores were calculated by the same person, and the heart rate (HR), pulse oximetry, and perfusion index (PI) were recorded at 2nd, 5th, and 10th min using a Masimo Radical-7 pulse co-oximetry with an adhesive sensor. The probe was placed preductally (on the right wrist) and then connected to the oximetry. The fraction of inspired oxygen (FiO2) was only 0.21 ("room-air") during all the stabilization period. In line with the NRP 2015 guideline,

aspiration was not routinely performed in the delivery room; the number of times that touch stimulation was required and the tactile stimulus time were recorded. Although electrocardiography (ECG) recommended in the latest guidelines and reads heart rate much faster, pulse oximetry had to be used in our study because the relationship between position and saturation and cerebral oximetry was evaluated.

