### **3.Cerebral oxygenation:**

Near-infrared spectroscopy (NIRS), which measures tissue oxygenation noninvasively, was used to evaluate cerebral oxygenation; the mean values at 5th and 10th min were recorded using a Covidien INVOS 5100C instrument. The cerebral regional cerebral oxygen saturation (rScO2) is the ratio of cerebral oxygenated hemoglobin (CHbO2) to the total oxygen bound to cerebral hemoglobin (CHb) and CHbO2 (rScO2 = CHbO2/CHb + CHbO2) . The rScO2 is the mean oxygen saturation of cerebral arterial, venule, and capillary blood; the venule data is predominate . Infrared light reveals the extent of saturation of the so-called watershed zone (a mixture of 33% arterial and 67% venous blood at a depth of 1-1,5 cm) . The NIRS probe was placed on both sides of the frontal lobe; the probe was cleaned before placement. The first measured value served as the basal value; rScO2 changes were then recorded at 2-s intervals to 60 s and the mean calculated. The cerebral rScO2 is normally 50-80, but may vary by 10-20% at any time . A decrease >20% for patients with a basal cerebral rScO2 value >50 and a decrease >15% for those with a basal cerebral rScO2 <50 indicate cerebral ischemia . Data were captured at 0.1 Hz and collected for 10 min, after application in each position consequently. Cerebral fractional oxygen extraction (cFOE) was calculated for 5th and 10th min average as ( (SpO2-rScO2)/SpO2 ) (SpO2: pulse oximetry oxygen saturation) for each position, which reflects the balance between oxygen delivery and consumption in the tissue .

An infant/pediatric sensor (Covidien INVOS 5100C) costs between \$110 and \$140 each. No outside funding was used for the budget in this study. Within the budget and time period, the maximum number of patients enrolled in the study.

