#### **4. Sample Size:**

In the investigators' center, monthly birth rate is 300 and since our hospital is the largest perinatology center in our region; the number of births with maternal and neonatal problems is high. When the investigators evaluated our records for the number of infants who were born  $> 37$  GA with CS under spinal anesthesia and did not require any resuscitation efforts; the number was approximately 15 per month. ( $P=0.05$ ) with a 2-sided a error of 5% and power of 80%, a total sample size of 37 total was required.

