### **Statistical Analyses:**

SPSS 25.0 (IBM Corporation, Armonk, New York, United States) and PAST 3 (Hammer, Ø., Harper, D.A.T., Ryan, P.D. 2001. Paleontological statistics) programs were used in the analysis of the variables. The conformity of univariate data to normal distribution was evaluated with the Shapiro-Wilk francia test, while homogeneity of variance was evaluated with the Levene test. Mardia for the conformity of multivariate data to normal distribution; while the (Dornik and Hansen omnibus) test was used, the Box-M test was used for variance homogeneity. In the comparison of more than two groups according to quantitative data, Fisher's Least Significant Difference (LSD) tests were used for One-Way Anova post hoc analysis, one of the parametric methods, Kruskal-Wallis H Test, which is one of the nonparametric tests, was used with the results of Monte Carlo simulation technique, and Dunn's Test was used for Post Hoc analyses. The Paired-Samples T test was tested using Bootstrap results, while the Wilcoxon Signed Ranks Test was tested using the monte carlo simulation method to compare two replicate measurements of dependent quantitative variables with each other. While Friedman's Two-Way test was tested using the monte carlo simulation method to test the variables with more than two repeated measurements and to examine the interaction according to the groups, the General Linear Model-Repeated Anova test from parametric methods was used, and the LSD test was used for Post Hoc analyses. In the comparison of categorical variables with each other, Fisher-Freeman-Holton test was tested with Monte Carlo Simulation technique. While quantitative variables were expressed as mean (standard deviation) and Median (Percentile 25 / Percentile 75) in the tables, categorical variables were shown as n (%). The variables were analyzed at 95% confidence level, and a p value less than 0.05 was considered significant.

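### One p<0.05 rule covers every variable, with no primary outcome, time point or multiplicity adjustment named in the available text, so the chance of a false position effect exceeds 5% once more than one test is made

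*Combined protocol and SAP*

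**What the plan says.** The Statistical Analyses section ends with a single criterion for all variables: "a p value less than 0.05 was considered significant". It ranks no outcome and mentions no adjustment across outcomes or times. Overall comparisons of positions use one-way ANOVA or Kruskal-Wallis. For pairwise work, "Fisher's Least Significant Difference (LSD) tests were used for One-Way Anova post hoc analysis"; Dunn's test follows Kruskal-Wallis, with no adjustment stated. For variables measured more than twice, the section describes Friedman's test and a repeated-measures ANOVA, the latter used "to examine the interaction according to the groups".

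Section 4, Sample Size, gives a total of 37 "with a 2-sided a error of 5% and power of 80" per cent, without an outcome, effect size or SD.

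The candidate outcomes are in two sections:

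- **Section 2, Medical records and vital parameters:** heart rate (HR), SpO2 and perfusion index (PI) at 2, 5 and 10 min; Apgar at 1 and 5 min; and the number and duration of tactile stimulations.
- **Section 3, Cerebral oxygenation:** rScO2 at 5 and 10 min, with a starting value as well ("The first measured value served as the basal value"), and oxygen extraction at the same two minutes ("Cerebral fractional oxygen extraction (cFOE) was calculated for" 5 and 10 min from SpO2 and rScO2).

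The nearest thing to a stated focus is a clause in section 2 explaining why pulse oximetry was used and not ECG: "because the relationship between position and saturation and cerebral oximetry was evaluated".

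**The concern.** With no designated primary, whichever variable and minute reaches p<0.05 can be presented as the effect of position. A reader of the results could not tell a planned finding from a selected one. The 5% error rate in the sample size statement belongs to a single test, and the analysis section does not say which test that is. A second, conditional question is whether LSD keeps the error at 5% among pairs of positions within one outcome.

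**Working it through.** **The plan's own figure.** The total of 37 cannot be reproduced, because its inputs are not given. Solving backwards for an overall F test at 80% power, 37 infants need a standardised effect (Cohen's f) of about 0.53 with three groups or 0.58 with four. Neither value is in the document, so the sample size does not reveal a primary outcome.

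**Counting the variables.** HR, SpO2 and PI at three times give 9; Apgar 2; stimulation count and time 2; rScO2 2; cFOE 2. The total is 9 + 2 + 2 + 2 + 2 = 17. How many would be tested as position effects depends on the reading:

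- 2 tests: SpO2 and rScO2, once each. This is the literal content of the clause in section 2.
- 3 tests: SpO2, rScO2 and cFOE, once each.
- 5 tests: SpO2 by one repeated-measures position test, and rScO2 and cFOE at each of two minutes (1 + 2 + 2).
- 7 tests: SpO2 at three minutes, rScO2 and cFOE at two (3 + 2 + 2).

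**Chance of at least one false position effect.** The inputs are α = 0.05 per test (Statistical Analyses), parallel groups of 15 (Materials and Methods), normal data and no effect of position. The correlation between tests is not in the document; 0 to 0.9 is assumed. For m independent tests the chance is 1 − 0.95^m. The correlated cases are simulated one-way F tests with 20,000 to 40,000 trials each.

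| Tests | Correlation 0 | 0.5 | 0.9 |
|---|---|---|---|
| 2 | 1 − 0.95² = 9.8% | 9% | 7% |
| 3 | 1 − 0.95³ = 14.3% | 13% | 9% |
| 5 | 1 − 0.95⁵ = 22.6% | 19% | 11% |
| 7 | 1 − 0.95⁷ = 30.2% | 24% | 12% |

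Three and four groups agree within about 1 point. Testing all 17 would give more than 7 tests do at the same correlation. One named outcome at one time with one overall test gives 5.0% (three groups) or 5.1% (four) in simulation.

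**Interaction tests.** A variable with three measurements analysed by repeated-measures ANOVA has two position-related tests, the group effect and the group-by-time interaction. The chance that either is falsely significant is 9.7% with three groups and 9.8% with four. This applies to HR, SpO2 and PI, and to rScO2 only if the starting value counts as a third measurement.

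**Pairwise contrasts within one outcome.** One position is shifted by 0.5 to 2 SD and the others are truly equal. The error is the chance of a false difference among the equal ones:

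- LSD after a significant F, three groups: 4–5%.
- LSD after a significant F, four groups: 7.7% at 0.5 SD, rising to about 12% from 1 SD upwards.
- Fisher-Hayter after a significant F, four groups: about 4–5%.
- Tukey after a significant F, four groups: about 3%.

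With the other positions equal, the pairwise difference detectable at 80% power with four groups is 1.11 SD for F-gated LSD, 1.20 SD for Fisher-Hayter and 1.28 SD for Tukey.

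**The case against.** **The outcomes are few in substance and strongly correlated.** This stands in part. cFOE is calculated from SpO2 and rScO2, and several variables repeat one measure over time, so the inflation may be near the low end. It approaches 5% only as the correlation approaches 1.

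**A reader might infer a false-positive rate near 58%.** That is 1 − 0.95^17. It needs all 17 variables to be independent and all to be claimed as position effects. The document supports neither: Apgar scores and stimulation measures are recorded without being given an efficacy role.

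**A reader might infer that every repeated variable gets a second, interaction test.** The text describes the repeated-measures methods for variables with more than two measurements. cFOE has two, and rScO2 has two unless the starting value counts. Friedman's test compares times within infants and is not a test of position.

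**The section 2 clause might be taken as an endpoint list.** It is not one. It justifies an instrument, names two measures, ranks neither and gives no minute.

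**LSD might be called invalid outright.** It is not: with three groups and an F gate it holds about 5%. The weakness exists only if right and left sides are separate groups, which the wording in Materials and Methods leaves open. Nor is Tukey the only remedy with four groups, since Fisher-Hayter also holds 5% and gives up less power.

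**A primary may have been named elsewhere.** Text before Materials and Methods was not available, so the claim is limited to what could be read. The two sections where a primary would be tied to power and testing are present and silent.

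**Conclusion.** The point holds. As written, the rule lets a false position effect appear more than 5% of the time on any of the readings set out above: about 7–10% for two tests and 12–30% for seven. The exact size cannot be known, because the number of tests and their correlation are not given.

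The figures rest on parallel groups of 15. Section 1 can be read as placing all infants supine, and section 3 speaks of recording "after application in each position consequently". If infants changed position, the figures do not apply, although the lack of a named primary remains. The LSD point is separate and conditional: up to about 12% error among truly equal positions with four groups, about 5% with three.

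**What to change.** 1. In Statistical Analyses, name one primary outcome at one time point, chosen by the sponsor, and cite the same outcome in Sample Size. Test its overall position effect at 0.05.
2. State whether there are three or four groups, and reconcile sections 1 and 3 with the allocation described in Materials and Methods.
3. Make pairwise contrasts only after a significant overall test. Use LSD with three groups; with four, a procedure that holds 5%, such as Fisher-Hayter or Tukey. If the primary is analysed by Kruskal-Wallis, use Holm-adjusted Dunn's tests.
4. Report all other variables, times and interactions as exploratory, with estimates and confidence intervals.
5. If reconciliation shows that infants changed position, keep the single primary and use within-infant tests.
6. Materials and Methods and Statistical Analyses are written in the past tense. If data have been seen, label the primary as post hoc and qualify the claims; the change cannot then restore prespecification.

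The cost is wording and, with four groups, a rise in the detectable pairwise difference from 1.11 SD (F-gated LSD) to 1.20 SD (Fisher-Hayter) or 1.28 SD (Tukey). With three groups, writing in the F gate costs nothing if one was intended; otherwise it moves LSD from 1.05 to 1.10 SD.
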